#### 10.1.1 Study Hypotheses

H1: PN recipients will have superior linkage and retention in: (a) OUD and other SUD treatment, (b) psychosocial services, and (c) pre/postnatal care compared to standard care.

H2: A larger portion of PN patients will be (a) MAT adherent and (b) drug abstinent compared to standard care.

H3: Higher levels of engagement/retention in care will positively moderate improvements in: (a) abstinence, (b) HIV/HCV risk behaviors, (c) depression/anxiety, and (d) child/mother outcomes (e.g., health care, NAS, stress).

### 10.2 Rationale for Sample Size and Statistical Power

#### 10.2.1 Projected Number of Sites

Two hospitals will be utilized as locations for identifying, recruiting, and engaging with potential project participants. Both hospital locations are major centers of activities for women's health within their respective health care systems. Both study hospitals are destination service centers for pregnant women to receive testing, care, and for eventual delivery. Specifically, Magee-Womens Hospital of UPMC is a hub for women's health care in Allegheny County as well as western PA. This hospital provides a number of health care services to pregnant women, including emergency department, obstetrics/gynecology, midwifery, and fertility services. The University of Utah is likewise a hub for care in Salt Lake City and the state of UT. This hospital is an urban level-1 trauma center with a number of services available for pregnant women, which include obstetrics/gynecology, midwifery, and fertility services.

#### 10.2.2 Projected Number of Participants per Site

Given this study is designed as a pilot study testing an expanded intervention and protocols/procedures, sample size is not based on a power estimate. Rather, our sample size is based on our estimates of how many patients can be screened and consented within the study timeframe, an appropriate method for pilot studies. Based on the above detailed counts of MAT inductions among pregnant women from Magee-Womens Hospital from 2013 and 2017, we anticipate an average of 141 potential women recruits each year. Further, based on the above described numbers of total pregnant women with OUD/overdose (i.e., poisoning) from the University of Utah from 2015-2017, we anticipate an average of 58 potential recruits each year. Therefore, if we screen and recruit patients across 15 months, and if 70% are eligible and interested, and of those, 70% provide informed consent; we will recruit a total of 122 patients in this study who will be randomized to the PN (n=61) or standard care conditions (n=61). *Importantly*, working to recruit, randomize, provide PN/standard care, and retain 122 pregnant women with OUD during the study timeframe will allow us sufficient time to learn to implement and manage this study across 2 sites in preparation for a subsequent fully-powered trial.

While definitive estimation and hypothesis testing are not the aim of this pilot study, the target sample sizes will allow estimation of odds ratios via 95% confidence intervals comparing outcome rates in the treatment and control arms, while accounting for within site clustering, with lower bounds differing from the odds ratio estimate by a factor of 1/3 to 1/2 and upper bounds differing from the odds ratio estimate by a factor of 2 to 3 for a broad range of overall rates, true odds ratios, and magnitude of site-to-site effects. In particular, the pilot study will allow detection of strong signals of preliminary benefit, and provide suggestions of benefit for more subtle signals.

Of the 122 women recruited to participate in this project, based on our preliminary information about patient flow at each site, we expect that 61 will be recruited at each site. For the 61 women recruited and randomized to the PN condition, we expect an equal recruitment distribution at each site. Based on estimates of a recruitment window of 15 months and active intervention delivery across 24 months, we will recruit approximately 5 participants between both sites. In terms of monthly caseload during the 6 busiest months of the study, each site will have approximately 9 to 12 active (pre and postnatal) participants at one time.

DSMB recommendation on November 1, 2019 was to evenly distribute recruitment goals for both sites. This is due to more outside agencies in Pennsylvania that are offering prenatal care and services for women with substance use disorders.

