- Study staff at both performance sites will also be trained to identify potentially eligible patients using patient medical records systems to locate women with OUD and who are pregnant (See Magee EMR review 1-2 and Utah EMR review). Once identified in the medical record systems, patients will be mailed a letter informing them they are eligible for a research study. Letters will be mailed to participants as much as weekly. Letters will not disclose how patients are possibly eligible in order to protect privacy. Patients will be invited to contact study staff to learn more about the study. Patients will also be informed in the letter that research staff will contact them after a week of not hearing back from them. After a week, research staff will reach out to potential patients.
- Study flyers will also be posted within the hospitals and clinics bulletin boards, waiting rooms of the performance sites and local outreach sites and facilities (see Advertisement). These flyers will contain general study information and study staff contact information.

Study staff who contact patients will do so from the University of Utah SUPeRAD clinic, staff research office space in Research park, staff office space from Magee Womens Research Institute or an appropriate and private location. Calls will be made from study use only cell phones or from office phones. Voicemail and other messaging is all password protected. If patients provide an email address, study staff may also contact them via this method. All computers and university related email accounts used to contact potential participants will be password protected.

Both sites will capture the number of eligible patients approached, number of patients approached, number of patients who chose to screen and those who did not. Reason for not screening will be captured. We will also capture the reason for why patients who were screened as ineligible were not eligible. Finally, we also capture the number of patients who chose to provide informed consent and those that did not. We will likewise capture the reasons patients may give for not providing informed consent and enrolling in the project. All these records will be captured using REDCap.

In order to ensure adequate follow up with participants; contact and locator information will be used to engage patients through multiple mediums, including phone, text, email, social media, and mail. See SOP for Continued Engagement.

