### **10.3 Statistical Methods for Primary and Secondary Outcomes**

We will employ descriptive statistics to calculate measures of central tendency, frequencies, and proportions for patient demographics and substance use, health, social, and mother/child indicators. T-tests and  $\chi^2$  tests will be used to assess mean and proportion differences between outcome variables by study group at each time point. Specifically, we will examine unadjusted differences between PN and standard care patients for linkage/retention in: (a) OUD and other SUD counseling, (b) psychosocial services, and (c) pre/postnatal care compared to standard care. We will also examine unadjusted differences between groups for MAT adherence, opioid and non-opioid drug abstinence, HIV/HCV risk behaviors, depression/anxiety, and child/mother outcomes (e.g., NAS, parental stress, attachment, and maternal social support).

We will also develop a series of multilevel models to examine treatment, time, and covariate effects associated with our primary and secondary study outcomes (Equation 1). The multilevel framework allows for a flexible treatment of time where change as a putative outcome may be nonlinear, accelerates, or decelerates at different rates across time. The framework is also forgiving of unequal numbers of observations and unequal spacing of observations across participants (i.e., missing data patterns). Models will be constructed using a model-building sequence proposed by Singer and Willett, in which: (a) empirical growth plots will be examined visually, (b) an unconditional model will be fit, (c) an unconditional linear growth model will be fit, (d) unconditional non-linear models (e.g., a piecewise model) will be fit, (e) the models' fit in the prior steps will be compared using the Akaike Information Criterion to determine the best growth model, and (f) time-invariant (e.g., baseline mental health diagnoses) and time-varying (e.g., drug use) predictors will be added to the models. We will examine the association of these predictors with the study outcomes across time. We will also test higher levels of service linkage/retention as moderators for improvements in (a) abstinence, (b) HIV/HCV risk behaviors, (c) depression/anxiety, and (d) child/mother outcomes.

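### Section 10.2.2 promises odds ratios with 95% confidence intervals, but 10.3 compares the arms with unadjusted significance tests not labelled exploratory, and section 10 does not analyse the recruitment and delivery data collected for the next trial.

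*Combined protocol and SAP*

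**What the plan says.** **Design rationale (10.2.2).** The plan states that "sample size is not based on a power estimate"; the number comes from expected recruitment. It adds "While definitive estimation and hypothesis testing are not the aim of this pilot study" and then describes the intended read-out: odds ratios between arms with 95% confidence intervals, allowing for clustering by site, with upper limits 2 to 3 times the estimate. It expects large signs of early benefit to be detectable and smaller ones only to be suggested. The same section gives learning to recruit, randomize, deliver care and retain women, ahead of a fully powered trial, as a reason for the design.

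**Hypotheses (10.1.1).** H1 is directional: "PN recipients will have superior linkage and retention". H2 is worded in the same way. Neither is marked exploratory.

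**Analysis (10.3).** T-tests and chi-square "tests will be used to assess mean and proportion differences between outcome variables by study group at each time point". The differences are described as unadjusted and cover all the listed primary and secondary outcomes. Multilevel models follow, with a logistic mixed model with random site effects as the example. Section 10.3 mentions no confidence interval, significance level or multiplicity rule.

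**Feasibility data.** Section 5.3 says "Both sites will capture the number of eligible patients approached, number of patients approached", and goes on to screening, consent and reasons for refusal. Section 7.5 describes a contact log for quantifying contact with each participant, and fidelity checks on recorded sessions. Section 10 analyses none of these.

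**The concern.** The rationale and the analysis describe different read-outs. One is an estimate with an interval; the other is a set of tests, in a trial that was not sized for testing and whose hypotheses are worded as superiority claims. Without an exploratory label or a commitment to intervals, nothing in 10.3 keeps a report from resting on which tests fell below 0.05. At this size such a report can mislead both ways: real effects of moderate size will often be missed, and many unadjusted tests will produce some false positives.

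Read literally, the tests also cover baseline. That assessment precedes randomization (7.4), so differences between the arms there arise only by chance, and testing them tells the reader nothing.

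The quantities that decide whether and how to run the full trial (the share eligible and interested, consent, accrual, sessions delivered, fidelity) have no planned estimate. The 70% and 70% assumptions behind the sample size are never set against what happens.

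**Working it through.** **1. The plan's own figures.** Inputs from 10.2.2: "we anticipate an average of 141 potential women recruits each year" (Magee), "we anticipate an average of 58 potential recruits each year" (Utah), and "if we screen and recruit patients across 15 months, and if 70% are eligible and interested, and of those, 70% provide informed consent".

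- Pool over 15 months: (141 + 58) × 15/12 = 248.75, about 249.
- Eligible and interested: 248.75 × 0.70 = 174.1.
- Consenting: 174.1 × 0.70 = 121.9. The stated 122 reproduces.

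Interval factor for an odds ratio with n = 61 per arm: exp(1.96 × √[1/(n p₁q₁) + 1/(n p₂q₂)]), no site effect, no loss, equal rates in both arms. This gives 2.03 at a rate of 50%, 2.43 at 20%, 2.87 at 13% and 3.26 at 10%. The stated factor of 2 to 3 therefore reproduces for rates of about 13% to 87%.

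**2. Power of one between-arm test.** The documents give no significance level, control rate or target effect. I assume a two-sided 5% level, control rates of 30% to 50% and no loss. Power = Φ[(d − 1.96 × SE₀)/SE₁], where d = p₂ − p₁, SE₀ = √[2p̄(1 − p̄)/61] with p̄ the mean of the two rates, and SE₁ = √[(p₁q₁ + p₂q₂)/61].

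| Control rate | PN rate at odds ratio 2.0 | d | SE₀ | SE₁ | Power |
|---|---|---|---|---|---|
| 30% | 46.2% | 0.162 | 0.0879 | 0.0867 | 45% |
| 40% | 57.1% | 0.171 | 0.0905 | 0.0892 | 47% |
| 50% | 66.7% | 0.167 | 0.0893 | 0.0880 | 46% |

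- For an odds ratio of 1.5 the same formula gives 18% to 20%.
- With an assumed 20% loss (49 per arm), power for 2.0 falls to about 38% to 40%.
- For control rates of 20% to 50%, 80% power needs a difference of about 23 to 25 points, an odds ratio of about 2.8 to 3.1.

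**3. False positives.** If each of the four primary domains in 4.1 were tested once at each of the three follow-ups at 5%, there would be 12 tests. Treated as independent, the chance of at least one false positive is 1 − 0.95¹² = 46%. The tests would in fact be correlated, so this is only a guide.

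**4. Precision of feasibility shares.** Half-width = 1.96 × √[p(1 − p)/N]. The 80% completion rate is assumed.

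| Quantity | N | p | Half-width |
|---|---|---|---|
| Eligible and interested | 249 | 70% | ±5.7 points |
| Consenting | 174 | 70% | ±6.8 points |
| Six-month completion, all | 122 | 80% | ±7.1 points |
| Six-month completion, one site or arm | 61 | 80% | ±10.0 points |

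**5. Where feasibility data are used.** Section 8.1.4 says the Study Completion Form enters analyses of treatment retention and completion. Section 12 has the study team and the DSMB review recruitment, accrual, retention and trial performance, as monitoring during conduct. Neither gives an analysis of the screening, eligibility and consent counts, the contact log or the fidelity checks.

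**The case against.** Three stronger readings are tempting, and the documents do not support them.

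- **That 10.3 contradicts 10.2.2 outright.** The disclaimer is of definitive estimation and testing. Exploratory tests are compatible with it.
- **That feasibility is the pilot's only aim, so the arms should not be compared.** Table 1 lists demonstrating preliminary benefit among three aims, and all four primary outcomes in 4.1 concern treatment, services or abstinence. Comparing the arms, even with directional hypotheses, is within scope.
- **That the read-out will be one underpowered p-value, taken as proof that PN does not work.** This is a prediction. Section 10.3 also plans descriptive statistics and multilevel models, and the logistic mixed model could yield the site-adjusted odds ratios that 10.2.2 promises.

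It is also fair to say that the low power is disclosed in substance. The sample size is openly not power-based, and the stated interval factor already implies that an estimated odds ratio of 2.0 would have an interval reaching 1. The 80% power at about 2.8 to 3.1 fits the plan's expectation of detecting only large effects. Section 8.1.4 partly covers retention and completion.

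What remains is narrower. Section 10.3 does not label the tests exploratory, does not commit to intervals, does not make the site-adjusted models the read-out, and by its wording includes baseline. Section 10 has no analysis of recruitment, consent, session delivery or fidelity. The baseline point rests on a literal reading, and its harm is small.

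**Conclusion.** The concern holds in this limited form. The trial remains valid and the arm comparison should stay, but the written analysis does not deliver the estimate-and-interval read-out that the design rationale promises, and it omits part of what the next trial needs.

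The size: about 45% to 47% power for an odds ratio of 2.0 with 61 per arm, so a single test would miss a true doubling of the odds slightly more often than it found it. This rests on an assumed two-sided 5% level, control rates of 30% to 50% and no loss; loss makes it worse. The feasibility shares, by contrast, can be estimated to about ±6 to ±7 points overall, and completion to about ±10 points by site, if the planned funnel and an 80% completion rate hold. This is a change that should be made, at low cost.

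**What to change.** In 10.3:

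1. Label the between-arm comparisons exploratory.
2. Replace the t-tests and chi-square tests with site-adjusted odds ratios, plus risk or mean differences as suits the outcome, with 95% confidence intervals at the three post-randomization assessments. State that no conclusion of benefit or of no benefit will be drawn from p < 0.05.
3. Describe baseline by arm without tests.
4. Add one table by site, with 95% intervals, giving:
   - the eligible-and-interested share and the consent share, each against the planned 70%;
   - enrolment per month;
   - prenatal sessions delivered relative to those available given gestational age at enrolment;
   - postnatal sessions delivered out of 4;
   - fidelity;
   - six-month completion by arm.

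Prenatal and postnatal sessions need separate denominators. Sections 3.2 and 7.5 give the prenatal number only as a maximum of 10, and 3.1 ties the prenatal span to gestational age at enrolment. A common denominator of 10 + 4 = 14 would make late enrollers look under-treated.

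The cost is the loss of headline p-values and one extra table. The data are already to be collected, and participants' care does not change.

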### **10.3 Statistical Methods for Primary and Secondary Outcomes**

We will employ descriptive statistics to calculate measures of central tendency, frequencies, and proportions for patient demographics and substance use, health, social, and mother/child indicators. T-tests and  $\chi^2$  tests will be used to assess mean and proportion differences between outcome variables by study group at each time point. Specifically, we will examine unadjusted differences between PN and standard care patients for linkage/retention in: (a) OUD and other SUD counseling, (b) psychosocial services, and (c) pre/postnatal care compared to standard care. We will also examine unadjusted differences between groups for MAT adherence, opioid and non-opioid drug abstinence, HIV/HCV risk behaviors, depression/anxiety, and child/mother outcomes (e.g., NAS, parental stress, attachment, and maternal social support).

We will also develop a series of multilevel models to examine treatment, time, and covariate effects associated with our primary and secondary study outcomes (Equation 1). The multilevel framework allows for a flexible treatment of time where change as a putative outcome may be nonlinear, accelerates, or decelerates at different rates across time. The framework is also forgiving of unequal numbers of observations and unequal spacing of observations across participants (i.e., missing data patterns). Models will be constructed using a model-building sequence proposed by Singer and Willett, in which: (a) empirical growth plots will be examined visually, (b) an unconditional model will be fit, (c) an unconditional linear growth model will be fit, (d) unconditional non-linear models (e.g., a piecewise model) will be fit, (e) the models' fit in the prior steps will be compared using the Akaike Information Criterion to determine the best growth model, and (f) time-invariant (e.g., baseline mental health diagnoses) and time-varying (e.g., drug use) predictors will be added to the models. We will examine the association of these predictors with the study outcomes across time. We will also test higher levels of service linkage/retention as moderators for improvements in (a) abstinence, (b) HIV/HCV risk behaviors, (c) depression/anxiety, and (d) child/mother outcomes.

Included below is the equation for a random-coefficient multilevel growth model. The  $Y$  in the equation represents a binary opioid abstinence outcome, for example, for the  $i$ th participants at time  $t$ . The symbol “~” indicates that the binary response with linear predictor given by the right hand side in the context of a logistic mixed effects model, with random effects for site, and potentially time within site. The primary variable types are represented in the equation: (a) *time* is

a variable representing time that may require multiple time variables in the event of nonlinear change (e.g. quadratic), (b) *time-varying* is any variable measured at each time point, and (c) *invariant* is a variable measured at the person-level. The model below can easily be extended to a third level if it is determined that there is variability in coefficients across centers.

	Level 1: $Y_{ti} \sim \beta_{0i} + \beta_{1i}time_{ti} + \beta_{2i}time\text{-}varying_{ti} + \beta_{3i}time_{ti}time\text{-}varying_{ti}$
Equation 1.	Level 2: $\beta_{0i} = \gamma_{00} + \gamma_{01}invariant_i + u_{0i}$
	$\beta_{1i} = \gamma_{10} + \gamma_{11}invariant_i + u_{1i}$

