## **3.0 STUDY DESIGN**

### **3.1 Overview of Study Design**

Opioid dependent pregnant women who present at Magee-Womens Hospital of UPMC and the University of Utah Hospital ≤32 weeks of gestation will be approached for potential participation in our OPTI-Mom 2.0 study. Our prenatal intervention is designed to span between 8 and 14 weeks and is dependent on gestational age at the time of enrollment. This allows study participants to receive the maximum amount of intervention sessions available prior to delivery. The following Approach Section describes preliminary data we have collected to support this proposal, project design, inclusion/exclusion criteria for participation, recruitment, intervention conditions, data collection/analysis, and timeline.

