### **5.1 Participant Inclusion Criteria**

This study will recruit women for participation meeting the following inclusion criteria:

- Adult ( $\geq 18$  years)
- English speaking
- Pregnant women (pregnancy status verified by gestational age  $>6$  weeks from last menstrual period confirmed by ultrasound)
- OUD verified by examination of medical records for an OUD diagnosis and the DSM Checklist (modified from the DSM-IV to confirm current diagnosis for substance use disorders)
- Plan to carry their babies to delivery verified by patient self report

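### The between-arm comparisons of linkage/retention name no adjustment for gestational age at enrolment, which gives up some precision where the outcome is a visit count

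*Combined protocol and SAP*

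**What the plan says.** Section 10.3 plans two layers of analysis and names neither as primary.

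- **Unadjusted.** The t- and chi-square "tests will be used to assess mean and proportion differences between outcome variables by study group at each time point". For the linkage/retention outcomes, "we will examine unadjusted differences between PN and standard care patients for linkage/retention".
- **Adjusted.** "We will also develop a series of multilevel models to examine treatment, time, and covariate effects associated with our primary and secondary study outcomes". The framework is described as "forgiving of unequal numbers of observations and unequal spacing of observations across participants". The one equation is a logistic mixed model, whose Y "in the equation represents a binary opioid abstinence outcome, for example". The predictors mentioned are examples (mental health diagnoses, drug use). Gestational age is not among them, and no count model, rate or offset is given.

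The assessment table in section 8.0 lists substance use treatment, psychiatric and social service visits, taken from records, as primary measures. Sections 4.1 and 10.1.1 make linkage/retention a primary outcome and the first hypothesis. They do not say whether it is a count, a rate or a yes/no variable.

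Entry requires a gestational age above 6 "weeks from last menstrual period confirmed by ultrasound" (section 5.1) and no later than week 32 (section 5.2). Section 3.1 gives a prenatal intervention of 8 to 14 weeks that "is dependent on gestational age at the time of enrollment". Section 10.1 stratifies randomisation by site only.

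**The concern.** A woman enrolled early in pregnancy has far longer to accrue prenatal visits than one enrolled at week 32. Randomisation balances this between arms on average, so an unadjusted comparison of mean counts is unbiased. The spread in observation time nevertheless stays in the error term and widens the confidence interval. The variable behind it is recorded at eligibility for everyone, so removing that noise costs no participants and no data collection. With 61 women per arm and a sample size fixed by feasibility, precision is one of the few things the trial can still improve. The pilot estimates are also meant to inform a fully powered trial (section 2.1).

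**Working it through.** **The plan's own figure.** Section 10.2.2: (141 + 58) × 15/12 × 0.70 × 0.70 = 121.9, which agrees with 122 (61 per arm). It rests on feasibility and is unaffected by this point.

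**Observation windows.** Entry from week 6 to week 32 is from the documents. Delivery at week 40, entry uniform over that range, and intervention length equal to the smaller of 14 weeks and the time to delivery are assumptions. Two months is taken as 8.7 weeks and six months as 26.

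| Window | Range (weeks) | Ratio |
|---|---|---|
| Entry to delivery | 40 − 32 = 8 to 40 − 6 = 34 | 4.25 |
| Prenatal intervention | 8 to 14 | 1.75 |
| Prenatal assessment to 2 months | 8.7 to 34 − 14 + 8.7 = 28.7 | 3.3 |
| Entry to 6 months | 34 to 60 | 1.76 |

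The first ratio is 3.9 with delivery at week 41 and 6.2 at week 37.

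**Share of count variance due to observation time.** Let r be the visit rate, c the between-woman CV of the rate, and M and V the mean and variance of observation time:

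share = r²V / [rM + r²V + c²r²(M² + V)]

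The documents give no value for r or c. Assume r = 0.5 per week and c = 0.6 or 1.0.

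- Entry to delivery: M = 21, V = 26²/12 = 56.3. At c = 0.6: 14.1 / (10.5 + 14.1 + 44.8) = 0.20. At c = 1.0: 14.1 / (10.5 + 14.1 + 124.3) = 0.095.
- Prenatal assessment to 2 months: 20/26 of women are spread evenly over 8.7 to 28.7 weeks and the rest sit at 8.7. So M = 8.7 + (20/26) × 10 = 16.4 and V = (20/26) × 400/3 − 7.69² = 43.4. Shares are 0.23 and 0.11.
- Prenatal intervention: M = 14 − (6/26) × 3 = 13.3, V = 2.3. Shares are 0.02 and 0.01.
- Entry to 6 months: M = 47, V = 56.3. Shares are 0.06 and 0.02.

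**Power.** Gamma-Poisson counts, 61 per arm, two-sided 5%, no site effect, 10,000 simulated trials per row. The t-test is compared with a linear model containing arm and gestational age at randomisation. The rate ratios are assumed.

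| Window | CV, rate ratio | t-test | Adjusted | Gain (points) |
|---|---|---|---|---|
| Entry to delivery | 0.6, 1.35 | 55.4% | 65.0% | 9.6 |
| Entry to delivery | 1.0, 1.65 | 64.9% | 69.1% | 4.2 |
| Prenatal assessment to 2 months | 0.6, 1.35 | 49.7% | 60.3% | 10.6 |
| Prenatal assessment to 2 months | 1.0, 1.65 | 61.9% | 66.8% | 4.9 |
| Prenatal intervention | 0.6, 1.35 | 63.7% | 63.6% | none |
| Prenatal intervention | 1.0, 1.65 | 71.0% | 70.6% | none |
| Entry to 6 months | 0.6, 1.35 | 70.1% | 72.1% | 2.0 |
| Entry to 6 months | 1.0, 1.65 | 73.6% | 73.8% | 0.2 |

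With no treatment effect, the adjusted test rejected in 4.7% to 5.4% of trials.

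**Hand check of the first row.** Power of 55.4% corresponds to a standardised effect of 1.96 + 0.136 = 2.096. Removing 20.3% of the variance gives 2.096 / √0.797 = 2.348, and Φ(2.348 − 1.96) = 65%.

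**Sensitivity.** The gain grows as women become more alike. At CV 0.5 and rate ratio 1.35, a separate simulation adjusting for observation time gave 65% to 78% for counts to delivery, and 69% to 72% if the prenatal window is spread uniformly over 8 to 14 weeks.

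**The case against.** Four points can be made for the plan, and each limits the finding.

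1. *Adjusted models are already planned.* This is correct. A reader might infer that the t-test is the only analysis, but the same section plans covariate-adjusted models for the primary and secondary outcomes. What remains is that gestational age is not named in them, the only written form is logistic, and neither layer is primary. The remark on unequal numbers and spacing concerns repeated assessments, not counts built up over unequal time.
2. *Visit counts are an inference.* Also correct. If linkage is yes/no, the chi-square test applies and the power figures above do not.
3. *Fourfold is not the documented prenatal window.* A reader might apply it to every comparison, but the prenatal assessment follows an intervention of 8 to 14 weeks. The spread then moves into the next interval, because the 2-month assessment is timed from delivery.
4. *This is a pilot with no power target, and hypothesis testing is not its aim.* That stands, and it keeps the point modest. Section 10.2.2 nevertheless expects to detect strong signals and get hints of weaker ones, so interval width matters.

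A reader might also infer that a rate model with log time at risk as offset is the natural remedy. The material does not support letting it lead. Delivery date and withdrawal come after randomisation, and pre-term birth is among the adverse events tracked in Appendix A. The robust offset test was also slightly liberal in simulation (6.6% against 5.7% for the t-test). If visits accrue mainly in the first 14 weeks, an offset of time to delivery lowers power from 63% to 58% at CV 0.6.

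**Conclusion.** The point holds as a loss of precision. Reading it as bias would be wrong, because randomisation balances gestational age on average and the unadjusted tests remain valid. For visit counts to delivery, or from the prenatal assessment to 2 months, naming this baseline covariate is worth about 4 to 10 points of power (10.6 in the largest simulated case). For the prenatal intervention window or the full follow-up to 6 months it is worth about 0 to 2 points. These sizes depend on an assumed visit rate, between-woman CV, rate ratio, uniform entry, delivery at week 40 and visits accruing in proportion to time, none of which the documents give. What comes from the documents is that the variable is available for every woman and is not a stratum, a named covariate or part of any outcome definition.

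**What to change.** In section 10.3:

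- State which linkage/retention outcomes are visit counts, and over which window.
- Make the between-arm comparison of those counts an adjusted one, with gestational age at randomisation and site (the stratification factor) as fixed baseline covariates. Either a linear model, which keeps the t-test's difference in means, or a count model allowing overdispersion with small-sample standard errors would serve.
- Keep the unadjusted t-tests and chi-square tests as descriptive.
- Name gestational age at randomisation as a person-level covariate in Equation 1 for the other primary outcomes. The gain there was not quantified.
- Use a log time-at-risk offset only as a sensitivity analysis.

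The cost is a change of wording and a little more analysis work. No new data are needed, and the sample size does not change.
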